**SpA features:**

- **Inflammatory back pain (IBP):** IBP according to experts: four out of five of the following parameters present: (1) onset before the age of 40 years, (2) insidious onset, (3) improvement with exercise, (4) no improvement with rest, (5) pain at night (with improvement upon getting up).
- **Arthritis:** Past or present active synovitis diagnosed by a doctor.
- **Enthesitis (heel):** Heel enthesitis: past or present spontaneous pain or tenderness at examination at the site of the insertion of the Achilles tendon or plantar fascia at the calcaneus.
- **Uveitis:** Past or present uveitis anterior, confirmed by an ophthalmologist.
- **Dactylitis:** Past or present dactylitis diagnosed by a doctor.
- **Psoriasis:** Past or present psoriasis diagnosed by a doctor
- **Crohn's/Colitis:** Past or present Crohn's disease or ulcerative colitis diagnosed by a doctor
- **Good response to NSAIDs:** At 24 to 48 h after a full dose of NSAID the back pain was not present anymore or much better.  
**Note:** As patients enrolling into the study should have failed 2 NSAIDs or be intolerant to NSAIDs, a doctor should assess whether patients had "good" prior response to NSAIDs.
- **Family history for SpA:** Presence in first-degree or second-degree relatives of any of the following: (a) ankylosing spondylitis, (b) psoriasis, (c) uveitis, (d) reactive arthritis, (e) IBD.  
**Note:** A doctor should confirm with his/her patient there was a clear diagnosis (not self-diagnosis) for any of these in first- or second-degree relatives.
- **HLA-B27:** positive testing according to standard laboratory techniques
- **Elevated CRP:** CRP >5.00 mg/L in the presence of back pain, after exclusion of other causes for elevated CRP concentration

**References:** Rudwaleit et al. 2009d; Sieper et al. 2009; Aydin et al. 2012.

---

**Appendix 6. Protocol Amendment I1F-MC-RHBX(b)  
Summary: A 52-Week Multicenter, Randomized, Double-  
Blind, Placebo-Controlled Study to Evaluate the Efficacy  
and Safety of Ixekizumab (LY2439821) in bDMARD-Naive  
Patients with Nonradiographic Axial Spondyloarthritis**

---

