### 6.3.1. Nonresponder Imputation

Analysis of categorical efficacy and health outcome variables will be assessed using a nonresponder imputation (NRI) method. Patients will be considered nonresponders for the NRI analysis if they do not meet the clinical response criteria or have missing clinical response data at the primary analysis time points. All nonresponders at Week 16 (Visit 8), as well as all patients who discontinue study treatment at any time prior to Week 16 for any reason, will be defined as nonresponders for the NRI analysis at Week 16. Similarly, all nonresponders at Week 52 (Visit 15), as well as patients who discontinue study treatment at any time prior to Week 52 for any reason, will be defined as nonresponders for the NRI analysis at Week 52. Patients who are deemed as inadequate responders by the investigator on or after Week 16 but remain on initially assigned blinded study treatment and only have modifications in concomitant medications will not influence whether or not a patient would be considered a nonresponder. Patients who stopped originally assigned blinded study treatment and use rescue ixekizumab 80 mg Q2W will be analyzed as nonresponders for the Week 52 analysis. They will be considered as nonresponders after the time of initiation of biologic rescue of ixekizumab 80 mg Q2W.

Randomized patients without at least 1 postbaseline observation will also be defined as nonresponders for the NRI analysis.

The NRI may be applied at any time point specified for analysis.

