Maastricht Ankylosing Spondylitis Enthesitis Score (MASES)	The MASES is an index used to measure the severity of enthesitis (Heuft-Dorenbosch et al. 2003). The MASES assesses 13 sites for enthesitis using a score of “0” for no activity, or “1” for activity. Sites assessed include: costochondral 1 (right/left), costochondral 7 (right/left), spinal iliaca anterior superior (right/left), crista iliaca (right/left), spina iliaca posterior (right/left), processus spinosus L5, and Achilles tendon proximal insertion (right/left).	MASES	The MASES is the sum of all site scores. Range: 0 to 13, higher scores indicate more severe enthesitis  0 = no activity 1 = activity	Missing if >20% (ie, ≥3) sites are missing. If ≤20% missing, then imputed sum = sum of scores from nonmissing sites x 13/ no. of nonmissing sites
		MASES change from baseline	Calculated as: observed MASES – baseline MASES	Missing if baseline or observed value is missing
		MASES score = 0	MASES score = 0 refers to complete resolution in enthesitis. Analysis of MASES score = 0 only applies to patients with baseline enthesitis (MASES >0).	Missing if observed value is missing
Spondyloarthritis Research Consortium of Canada (SPARCC) enthesitis	SPARCC enthesitis is an index used to measure the severity of enthesitis (Maksymowych et al. 2009). The SPARCC assesses 16 sites for enthesitis using a score of “0” for no activity, or “1” for activity. Sites assessed	SPARCC enthesitis	The SPARCC is the sum of all site scores Range: 0–16, higher scores indicate more severe enthesitis.	Missing if >20% (ie, ≥4) sites are missing. If ≤20% missing, then imputed sum = sum of scores from nonmissing sites x 16/ no. of nonmissing sites.

Measure	Description	Variable	Derivation / Comment	Imputation Approach if with Missing Components
	include Medial epicondyle (left/right [L/R]), Lateral epicondyle (L/R), Supraspinatus insertion into greater tuberosity of humerus (L/R), Greater trochanter (L/R), Quadriceps insertion into superior border of patella (L/R), Patellar ligament insertion into inferior pole of patella or tibial tubercle (L/R), Achilles tendon insertion into calcaneum (L/R), and Plantar fascia insertion into calcaneum (L/R).	SPARCC enthesitis change from baseline	Calculated as: observed SPARCC enthesitis – baseline SPARCC enthesitis	Missing if baseline or observed value is missing

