		SPARCC enthesitis score = 0	SPARCC enthesitis score = 0 refers to complete resolution in enthesitis. Analysis of SPARCC enthesitis score = 0 only applies to patients with baseline enthesitis (SPARCC enthesitis >0).	Missing if observed value is missing
Tender Joint Count (TJC)	The number of tender and painful joints will be determined by examination of 46 joints (23 joints on each side of the patient’s body). The 46 joints are assessed and classified as tender or not tender.	TJC total score	Adjusted sum of the pain/tenderness for all 46 joints: $\left( \frac{\text{sum of all joints checked to be painful/tender}}{\text{number of evaluable joints}} \right) \times 46$ See Appendix 4 for details.	If more than half of the joint scores are non-evaluable, the total score will be missing.
		TJC change from baseline	Calculated as: observed TJC – baseline TJC only applies to patients whose baseline TJC >0.	Missing if baseline or observed value is missing
		Proportion of patients with TJC = 0 when baseline TJC > 0	Analysis of TJC = 0 only applies to patients whose baseline TJC > 0.	Missing if observed value is missing

Measure	Description	Variable	Derivation / Comment	Imputation Approach if with Missing Components
		Proportion of patients with TJC = 0 for patients with current or historical peripheral arthritis at baseline	Analysis of TJC = 0 only applies to patients with current or historical peripheral arthritis at baseline	Missing if observed value is missing
Swollen Joint Count (SJC)	The number of swollen joints will be determined by examination of 44 joints (22 joints on each side of the patient’s body). The 44 joints are assessed and classified as swollen or not swollen.	SJC total score	Adjusted sum of the pain/tenderness for all 44 joints. $\left( \frac{\text{sum of all joints checked to be swollen}}{\text{number of evaluable joints}} \right) \times 44$ See Appendix 4 for details.	If more than half of the joint scores are nonevaluable, the total score will be missing.
		SJC change from baseline	Calculated as: observed SJC – baseline SJC Only applies to patients whose baseline SJC >0.	Missing if baseline or observed value is missing
		Proportion of patients with SJC = 0 when baseline SJC > 0	Analysis of SJC = 0 only applies to patients whose baseline SJC > 0.	Missing if observed value is missing

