Enthesitis Scores	MASSES and SPARCC change from baseline	MMRM	ITT Population with Baseline MASSES >0 (or SPARCC >0)	IXE80Q2W & IXE80Q4W vs. placebo at Weeks 16 and 52 and all other postbaseline visits in Period 2	Other secondary efficacy analyses (Section 6.10.4).
		ANCOVA with mBOCF	ITT Population with Baseline MASSES >0 (or SPARCC >0)	IXE80Q2W & IXE80Q4W vs. placebo at Weeks 16 and 52 and all other postbaseline visits in Period 2	Other secondary efficacy analyses (Section 6.10.4).

Measure	Variable	Analysis Method (Sections 6.1 and 6.3)	Population (Section 6.1.1)	Comparison/Time Point	Analysis Type
		ANCOVA with mBOCF	ITT Population with Current or Historical Enthesitis at Baseline	IXE80Q2W & IXE80Q4W vs. placebo at Weeks 16 and 52 and all other postbaseline visits in Period 2	Other secondary efficacy analyses (Section 6.10.4).
	MASES score = 0 (similarly SPARCC = 0)	Logistic regression analysis with NRI; Fisher's exact test with NRI	ITT Population with Baseline MASES >0 (or SPARCC >0)	IXE80Q2W & IXE80Q4W vs. placebo at Weeks 16 and 52 and all other postbaseline visits in Period 2	Other secondary efficacy analyses (Section 6.10.4).
		Logistic regression analysis with NRI; Fisher's exact test with NRI	ITT Population with Current or Historical Enthesitis at Baseline	IXE80Q2W & IXE80Q4W vs. placebo at Weeks 16 and 52 and all other postbaseline visits in Period 2	Other secondary efficacy analyses (Section 6.10.4).
Peripheral Arthritis	TJC and SJC change from baseline	MMRM	ITT Population with baseline TJC >0 (or SJC >0)	IXE80Q2W & IXE80Q4W vs. placebo at Weeks 16 and 52 and all other postbaseline visits in Period 2	Other secondary efficacy analyses (Section 6.10.4).
		ANCOVA with mBOCF	ITT Population with baseline TJC >0 (or SJC>0)	IXE80Q2W & IXE80Q4W vs. placebo at Weeks 16 and 52 and all other postbaseline visits in Period 2	Other secondary efficacy analyses (Section 6.10.4).
		ANCOVA with mBOCF	ITT Population with Current or Historical Enthesitis at Baseline	IXE80Q2W & IXE80Q4W vs. placebo at Weeks 16 and 52 and all other postbaseline visits in Period 2	Other secondary efficacy analyses (Section 6.10.4).
	TJC = 0 when baseline TJC > 0 (similarly SJC = 0 when baseline SJC > 0)	Logistic regression analysis with NRI; Fisher's exact test with NRI	ITT Population with Baseline TJC>0 (or SJC>0)	IXE80Q2W & IXE80Q4W vs. placebo at Weeks 16 and 52 and all other postbaseline visits in Period 2	Other secondary efficacy analyses (Section 6.10.4).

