Measure	Variable	Analysis Method (Sections 6.1 and 6.3)	Population (Section 6.1.1)	Comparison/Time Point	Analysis Type
	TJC = 0 when patients had current or historical peripheral arthritis at baseline (similarly SJC = 0 when patients had current or historical peripheral arthritis at baseline)	Logistic regression analysis with NRI; Fisher’s exact test with NRI	ITT Population with Current or Historical Peripheral Arthritis at Baseline	IXE80Q2W & IXE80Q4W vs. placebo at Week 16 and 52 and all other postbaseline visits in Period 2	Other secondary efficacy analyses (Section 6.10.4).
Anterior uveitis	Crude and exposure-adjusted incidence rates for patients with anterior uveitis	Fisher’s exact test and Poisson regression	ITT Population	IXE80Q2W & IXE80Q4W vs. placebo during Period 2	Other secondary efficacy analyses (Section 6.10.4).
NSAID (including COX-2 inhibitor) Intake	Proportion of patients taking NSAID (including COX-2 inhibitor)	Descriptive statistics	ITT Population	At Baseline (Week 0), Weeks 16, 20, 24, 28, 32, 36, 44, 52.	Analyses on NSAID intake (Section 6.10.4.1)
	Change from baseline in ASAS-NSAID	Descriptive statistics	ITT Population who have NSAID (including COX-2 inhibitor) intake at Baseline	At Weeks 16, 20, 24, 28, 32, 36, 44, 52.	Analyses on NSAID intake (Section 6.10.4.1)

Measure	Variable	Analysis Method (Sections 6.1 and 6.3)	Population (Section 6.1.1)	Comparison/Time Point	Analysis Type
	ASAS-NSAID50	Descriptive statistics	ITT Population who have NSAID (including COX-2 inhibitor) intake at Baseline	At Weeks 16, 20, 24, 28, 32, 36, 44, 52.	Analyses on NSAID intake (Section 6.10.4.1)

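### MASES = 0 and SPARCC enthesitis = 0 are also tested in patients with current or past enthesitis, against the SAP's own rule that limits these analyses to a baseline score above 0

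*SAP*

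**What the plan says.** SAP Table RHBX.6.4 gives the variable its meaning: "MASES score = 0 refers to complete resolution in enthesitis". It also fixes who is analysed: "Analysis of MASES score = 0 only applies to patients with baseline enthesitis (MASES >0"). The SPARCC enthesitis entry has the same rule: "Analysis of SPARCC enthesitis score = 0 only applies to patients with baseline enthesitis (SPARCC enthesitis >0").

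SAP Table RHBX.6.5 then lists two populations for the score = 0 response, each with logistic regression and Fisher's exact test under NRI, at Weeks 16 and 52 and the other postbaseline visits. The first follows the rule: "ITT Population with Baseline MASES >0 (or SPARCC >0"). The second is the "ITT Population with Current or Historical Enthesitis at Baseline". That label also appears in change-from-baseline rows of the same table, which are not at issue here.

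SAP Section 6.3.1 sets the imputation: "Patients will be considered nonresponders for the NRI analysis if they do not meet the clinical response criteria or have missing clinical response data". Patients who stop study treatment before the time point are nonresponders, and so are rescued patients once ixekizumab rescue has started. Baseline status plays no part in the rule.

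**The concern.** A resolution endpoint needs something to resolve. The second population admits patients whose enthesitis was over before the trial and who score 0 at baseline. They meet the response criterion by staying where they started, and lose it through rescue, discontinuation or missing data as well as through new enthesitis. For them the endpoint largely records whether they remained on assigned treatment with data at the visit.

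The trial report could then carry two results for one variable, one of which is resolution and one of which is not. A programmer also cannot follow both tables as written.

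**Working it through.** The documents give no response rate, sample size or power for these variables, so there is no figure to reproduce. The main check sets the tables side by side.

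**1. Do the tables conflict?** Table RHBX.6.4 limits the analysis to a baseline score above 0. The second row of Table RHBX.6.5 carries no such limit. If the limit applied there too, the row would hold only patients already in the first row. It has a purpose only if baseline-0 patients are admitted, and Table RHBX.6.4 rules them out.

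**2. Can baseline-0 patients be in the second population?** Yes.
- The label itself covers past disease. The protocol's SpA feature (Appendix 5) is met by history alone: "Heel enthesitis: past or present spontaneous pain or tenderness at examination".
- That feature includes the plantar fascia, which is among the SPARCC sites but not among the 13 MASES sites. Even a patient with current heel enthesitis can score MASES 0.

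**3. Which way does the result move?** Let h be the share of the analysed population with baseline score 0, p the resolution rate when the baseline score is above 0, and q the chance that a baseline-0 patient counts as 0 at the visit after NRI. T is ixekizumab, C is placebo.

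- Arm rate = (1 − h) × p + h × q
- Difference = (1 − h) × (pT − pC) + h × (qT − qC)

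The difference shrinks when qT − qC is smaller than pT − pC, is unchanged when they are equal, and grows when it is larger.

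**4. Illustration.** All inputs are assumptions: pT = 45%, pC = 25%, and 60 patients per arm with baseline score above 0. Power is two-sided at 0.05 by normal approximation. Restricted to baseline above 0, the difference is 20 points, the odds ratio 2.45 and the power 63%.

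With q = 85% in both arms and n = 60 / (1 − h) per arm:

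| h | n per arm | Rates T v C | Difference | Odds ratio | Power |
|---|---|---|---|---|---|
| 10% | 67 | 49% v 31% | 18 points | 2.14 | 57% |
| 20% | 75 | 53% v 37% | 16 points | 1.92 | 50% |
| 30% | 86 | 57% v 43% | 14 points | 1.76 | 45% |
| 40% | 100 | 61% v 49% | 12 points | 1.63 | 40% |

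At h = 30%, for example, the ixekizumab rate is 0.7 × 0.45 + 0.3 × 0.85 = 0.57 and the placebo rate is 0.7 × 0.25 + 0.3 × 0.85 = 0.43. At h = 50% the difference would be 10 points and the odds ratio 1.52. No power is shown there, because 60 / 0.5 = 120 per arm exceeds the planned 100.

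Now let NRI remove more placebo patients:
- With q = 85% v 65%, the difference is (1 − h) × 20 + h × 20 = 20 points at every h.
- With q = 85% v 55%, it is 20 + 10h points: 21 at h = 10% and 24 at h = 40%.

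In both cases the contrast contributed by baseline-0 patients can come from rescue or discontinuation, with no enthesitis resolving.

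**The case against.** Four things can be said for the plan.

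- **The properly restricted analysis is there.** It stands directly above the contested row, which is labelled only by the score. The resolution wording sits in Table RHBX.6.4 beside the baseline restriction. This stands and limits the harm, but does not remove the conflict.
- **The stakes are low.** These are other secondary analyses with no multiplicity adjustment (SAP Section 6.10.4) and they enter neither testing scheme in Section 6.5. This stands too.
- **The row may be intended.** The revision history records that the enthesitis analyses in Tables 6.4 and 6.5 were updated, so one sentence in Table RHBX.6.4 may simply have been left behind. That is possible, and it is why relabelling is offered as well as deletion. It does not make a patient who scores 0 throughout a case of resolution.
- **The mixture is hypothetical.** SAP Section 6.7.1 records a history of enthesitis separately from baseline scores above 0, and nothing says that one group contains the other. This stands: the table above shows direction and scale and is not an estimate.

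A reader might also infer that the joint-count analyses share the fault, because TJC = 0 and SJC = 0 are tested in the "ITT Population with Current or Historical Peripheral Arthritis at Baseline". The documents do not support that. Table RHBX.6.4 defines separate variables for that group, they match Table RHBX.6.5, and they are not called resolution. The SAP also lists incidence of peripheral arthritis among its other secondary analyses, and patients with no affected joint at baseline are relevant to incidence.

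**Conclusion.** For MASES = 0 and SPARCC enthesitis = 0, Tables RHBX.6.4 and RHBX.6.5 contradict each other. This follows from the text and needs no assumption. The result in the wider population cannot be read as resolution, whichever way it moves.

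A reader might infer that the wider population must dilute the treatment difference. That holds only if baseline-0 patients keep a score of 0 about equally often in both arms after NRI, which is most plausible at Week 16, before rescue can take effect. The difference is then multiplied by (1 − h). By Week 52, unequal rescue or dropout could hold it up or inflate it. The share h and all the rates are unknown, so the size of the distortion is unknown.

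The effect is confined to other secondary analyses. No primary or major secondary conclusion depends on it, and the TJC = 0 and SJC = 0 rows need no change.

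**What to change.** Do one of the following in the SAP:

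1. Delete the current-or-historical population from the MASES = 0 and SPARCC = 0 rows of Table RHBX.6.5, leaving the baseline-above-0 analysis that Table RHBX.6.4 requires.
2. Keep the wider population, rename the variable as free of enthesitis at the visit, report it descriptively and split by baseline score (0 and above 0), and amend Table RHBX.6.4 to define that second variable.

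The first option costs only table wording and removes analyses. The second adds one definition and a split in the output. Neither needs new data or touches the testing schemes.

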### **6.10.1. Primary Outcome and Methodology**

The primary outcomes are the proportion of patients achieving ASAS40 at Week 16 (Visit 8) for regulatory agencies that accept Week 16 as primary endpoint, and ASAS40 at Week 52 (Visit 15) for regulatory agencies that require Week 52 as primary endpoint. These are de-facto (effectiveness) estimands (that is, the effect attributable to the originally randomized treatment, ixekizumab 80 mg Q2W, ixekizumab 80 mg Q4W, and placebo, at the primary time points of Week 16 and Week 52 in all randomized patients). For inadequate responders who were treated with biologic rescue of ixekizumab 80 mg Q2W, only data up to the time of initiation of biologic rescue of ixekizumab 80 mg Q2W will be included in the primary analysis. These patients will be considered nonresponders to categorical assessment per the NRI imputation method after initiation of biologic rescue with ixekizumab 80 mg Q2W.

The primary analysis will be based on the ITT Population for Period 2 comparing each ixekizumab treatment group and placebo at Week 16 (Visit 8) and at Week 52 (Visit 15). The primary analysis is a logistic regression analysis with treatment, geographic region, and screening MRI/CRP status in the model (Section 6.1.2).

In the primary analysis, treatment groups of ixekizumab 80 mg Q2W and Q4W will be analyzed without regard to starting dose. The primary comparison will be tested based on the graphical multiple testing procedures detailed in Section 6.5.

[Table RHBX.6.5](#) provides the detailed analyses including analysis type, method and imputation, population, time point, and treatment comparisons for primary outcome.

